## 2.8.4 Other safety data

### 2.8.4.1 ECG data

12-lead ECGs including PR, QRS, QT, QTcF intervals, and HR will be obtained for each subject during the study. ECG data will be read and interpreted locally. The average of the ECG parameters at each assessment should be used in the analyses.

The number and percentage of subjects with notable ECG values will be presented.

- QT, or QTcF
  - New value of  $> 450$  and  $\leq 480$  ms
  - New value of  $> 480$  and  $\leq 500$  ms
  - New value of  $> 500$  ms
  - Increase from baseline of  $> 30$  ms to  $\leq 60$  ms
  - Increase from baseline of  $> 60$  ms
- HR
  - Increase from baseline  $> 25\%$  and to a value  $> 100$  bpm
  - Decrease from baseline  $> 25\%$  and to a value  $< 50$  bpm

- PR
  - Increase from baseline >25% and to a value > 200 ms
  - New value of > 200 ms
- QRS
  - Increase from baseline >25% and to a value > 120 ms
  - New values of QRS > 120 ms

ECGs collected during on-treatment will be summarized. The number and percentage of subjects with notable ECG values will be presented for the safety set. A listing of subjects with notable ECGs will be provided and value measure during the post-treatment follow up will be flagged in the listing.

#### 2.8.4.2 Vital signs

Vital sign assessments are performed to characterize basic body function. The following parameters were collected: height (cm), weight (kg), body temperature (°C), heart rate (beats per minute), systolic and diastolic blood pressure (mmHg).

Vital signs collected during on-treatment will be summarized. Values measured during the post-treatment period will be flagged in the listings. The number and percentage of subjects with notable vital sign values (high/low) will be presented. A listing of subjects with notable vital signs will be provided and value measure during the post-treatment follow up will be flagged in the listing.

**Table 2-3 Criteria for notable vital sign values**

Vital sign (unit)	Notable high value	Notable low value
Weight (kg)	increase > 10% from Baseline	decrease > 10% from Baseline
Systolic blood pressure (mmHg)	>=180 with increase from baseline of $\geq 20$	<=90 with decrease from baseline of $\geq 20$
Diastolic blood pressure (mmHg)	>=105 with increase from baseline of $\geq 15$	<=50 with decrease from baseline of $\geq 15$
Pulse rate (bpm)	>=100 with increase from baseline of >25%	<=50 with decrease from baseline of > 25%
Body temperature (°C)	>= 39.1°C	-

#### 2.9 Pharmacokinetic endpoints

All PK concentration analyses and PK concentration summary statistics will be based on the INC-PAS and PDR-PAS. PK parameters summary statistics will be based on the INC-FPAS and PDR-FPAS.

#### PK parameters

Pharmacokinetic parameters will be determined by non-compartmental method(s) using the pharmacokinetic profile of capmatinib and spartalizumab. PK parameters listed in [Table 2-4](#) will be derived and reported, when feasible.

**Table 2-4 Non-compartmental pharmacokinetic parameters for capmatinib and spartalizumab**

AUClast	The AUC from time zero to the last measurable concentration sampling time (tlast) (ng x hr x mL-1 for capmatinib; µg x day x mL-1 for spartalizumab)
AUCtau	The AUC calculated to the end of a dosing interval (tau) at steady-state (ng x hr x mL-1 for capmatinib; µg x day x mL-1 for spartalizumab)
Cmax	The maximum (peak) observed plasma, blood, serum, or other body fluid drug concentration after single dose administration (ng/mL for capmatinib; µg/mL for spartalizumab)
Tmax	The time to reach maximum (peak) plasma, blood, serum, or other body fluid drug concentration after single dose administration (hr for capmatinib; day for PDR)

Descriptive statistics will be presented for all pharmacokinetic parameters, as described below.

**Table 2-5 Descriptive analysis**

Parameters	Descriptive statistics
AUC  , C max ,	Mean standard deviation, CV% mean, geometric mean, CV% geo-mean, median, minimum, and maximum. 90% CI for R acc .
T max	Median, minimum, and maximum.

 Includes, AUCtau, AUClast (or all AUC parameters)  
CV% = coefficient of variation (%) = sd/mean\*100  
CV% geo-mean = sqrt (exp (variance for log transformed data)-1) \*100

Missing PK parameter values will not be imputed. A listing of derived PK parameters per subject will be produced.

## Concentrations

PK concentration data for each compound will be listed for all subjects by visit/sampling time point. Descriptive summary statistics will be provided by visit/sampling time point for all subjects, including the frequency (n, %) of concentrations below the lower limit of quantification (LLOQ) and reported as non-zero.

Summary statistics will include mean (arithmetic and geometric), SD, CV (arithmetic and geometric), median, minimum and maximum.

Descriptive graphical plots of individual concentration versus time profiles and mean concentration versus time profiles will be generated.

### 2.9.1 Data handling principles

All concentrations below the lower limit of quantitation (LLOQ) or missing data will be labeled as such in the concentration data listings. Concentrations below the LLOQ will be treated as zero in summary statistics and for the calculation of pharmacokinetic parameters, unless otherwise stated under the Pharmacokinetic Analysis Set. Concentrations below LLOQ will be treated as zero in summary statistics and for PK parameter calculations. Zero concentrations will not be included in the geometric mean and geometric CV% calculations.

Missing values for any PK data will not be imputed and will be treated as missing.

At the time of analysis, concentration data from subjects may be removed from the estimation of certain PK parameters depending on the number of available blood samples, concomitant medications, vomiting, etc. Specific time points might be removed from the analysis set if technical issues with the sample are reported (e.g., sampling issues, missing information). These subjects and concentration data points will be identified at the time of analysis.

Final

## 2.14 Interim analysis

No formal interim analysis is planned.

## 3 Sample size calculation

No formal statistical power calculations to determine sample size were performed for this part of the study.

Approximately 30 subjects are planned to be treated in Part 1 of the study. [Table 3-1](#) shows the probability to detect a significant effect under different true ORR i.e., Probability to have ORR  $\geq 55\%$  and the lower bound of the 95% CI  $> 35\%$ . If the true ORR is 67% there is 91.7% probability that the single arm run-in part will be declared a success with 30 subjects.

**Table 3-1 Design operating characteristics**

True ORR	N	Minimum number of responses to declare success	ORR (95% CI)	Probability to reject H0
55%	30	17	56.7% (37.4 - 74.5)	50.2%
60%				71.5%
67%				91.7%

## 4 Change to protocol specified analyses

Not applicable.

## 5 Appendix

### 5.1 Imputation rules

#### 5.1.1 Study drug

##### 5.1.1.1 Data Imputation for the last administration

The following rule should be used for the imputation of date of last administration for a given study treatment component:

**Scenario 1:** If the date of last administration is completely missing and there is no EOT eCRF page, the subject is considered as on-going:

The subject should be considered as on treatment. In this case, the cut-off date should be used as the last dosing date for exposure calculations.

**Scenario 2:** If the date of last administration is completely or partially missing and the EOT eCRF page is available (prior to any death date or withdrawal of consent date, if available):

Case 1: The date of last administration is completely missing, and the EOT visit date is complete, then this latter date should be used.

Case 2: Only Year(yyyy) of the dose end date is available and yyyy < the year of EOT date:

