## Study Update

As of 28-Jul-2021 when enrollment was halted, 28 patients were treated with capmatinib plus spartalizumab and 3 patients were in screening in the run-in part (Part 1) of the study. The patients who were on combination treatment have discontinued spartalizumab and are continuing on capmatinib single agent since the enrollment halt. The patients who were in screening at the time of the enrollment halt have started receiving capmatinib single agent treatment. As of 06-Sep-2021, 19 patients were still on treatment with capmatinib.

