### 6.7.2 Instruction for prescribing and taking study treatment

Following the study enrollment halt, spartalizumab treatment has been discontinued in all ongoing subjects.

The dose and treatment schedule of each investigational drug used in this study is described in [Table 6-5](#).

All kits of study treatment assigned by the IRT will be recorded in the IRT system.

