### 8.5.2.3 Pharmacokinetic [REDACTED] sampling for spartalizumab

Following the approval of protocol amendment 01, PK [REDACTED] sampling for spartalizumab will not be performed, except in the event of a clinically significant AE or if [REDACTED] is suspected up to 150 days from last dose of spartalizumab.

Blood samples for spartalizumab PK [REDACTED] analysis will be collected for all the subjects as outlined in [Table 8-9](#) and [Table 8-10](#). PK [REDACTED] samples will be collected at the time of study treatment discontinuation (EOT visit) or when spartalizumab treatment is discontinued (in case spartalizumab is prematurely discontinued due to toxicity). The 150-days safety follow-up sample will only be collected if the visit is performed at site. Extensive PK samples will be collected in cycle 3 from the first fifteen subjects enrolled in Part 1. PK [REDACTED] samples will be collected also in the event of a clinically significant AE (such as infusion reaction/anaphylaxis) or if [REDACTED] is suspected. No additional PK [REDACTED] samples will be collected after the cut-off of the primary CSR.

**Table 8-9 Spartalizumab pharmacokinetic [REDACTED] blood collection log for extensive PK sample collection (first 15 subjects of Part 1) - obsolete upon approval of protocol amendment 01**

Cycle	Day	Scheduled Time (h)	Analytes
1	1	Pre-dose 	PK [REDACTED]
3	1	Pre-dose 	PK [REDACTED]
3	1	1h ( $\pm 5$ min)	PK
3	4	72h ( $\pm 8$ h)	PK
3	8	168h ( $\pm 8$ h)	PK
3	15	336h ( $\pm 24$ h)	PK
4	1	Pre-dose 	PK [REDACTED]
6	1	Pre-dose 	PK [REDACTED]

Cycle	Day	Scheduled Time (h)	Analytes
Every 12 cycles after C6D1 until discontinuation of spartalizumab treatment	1	Pre-dose 	PK [REDACTED]
EOT 		anytime	PK [REDACTED]
150-day safety follow-up 		anytime	PK [REDACTED]
Unscheduled		anytime	

 Take samples immediately prior to infusion of spartalizumab

 Samples to be collected at the time of study treatment discontinuation (EOT visit) or when spartalizumab treatment is discontinued

 Only applicable for subjects who return to the site for 150-day safety FU visit

**Table 8-10      Spartalizumab/placebo pharmacokinetic [REDACTED] blood collection log for non-extensive PK collection (remaining subjects of Part 1 and all Part 2 subjects) - obsolete upon approval of protocol amendment 01**

Cycle	Day	Scheduled Time (h)	Analytes

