## 9 Study discontinuation and completion

### 9.1 Discontinuation

#### 9.1.1 Discontinuation of study treatment

Discontinuation of study treatment for a subject occurs when study treatment is stopped, and can be initiated by either the subject or the investigator.

The investigator must discontinue study treatment for a given subject if, he/she believes that continuation would negatively impact the subject's well-being. An end of treatment visit will be performed when subjects permanently discontinue the study treatment to which they were assigned at study entry.

Study treatment must be discontinued under the following circumstances:

- Disease progression per RECIST 1.1 as determined by investigator assessment (with or without confirmation by BIRC). In some circumstances subjects may be allowed to continue to receive study treatment beyond disease progression as per RECIST 1.1. These subjects will continue assessments as outlined in [Table 8-1b](#) and will complete the EOT visit only after permanent discontinuation of study treatment (see [Section 6.1.4](#))
- Subject/guardian decision
- Investigator decision
- Any situation in which study participation might result in a safety risk to the subject.
- Protocol deviation that results in a significant safety risk to the subject
- Adverse event requiring permanent discontinuation of study treatment (see [Table 6-3](#))
- Pregnancy
- Death

If discontinuation of study treatment occurs, the investigator should make a reasonable effort to understand the primary reason for the subject's premature discontinuation of study treatment and record this information.

Subjects who discontinue study treatment or who decide they do not wish to participate in the study further should NOT be considered withdrawn from the study UNLESS they withdraw their consent (see [Section 9.1.2](#)). **Where possible, they should return for the assessments indicated** in the assessment schedule. If they fail to return for these assessments for unknown

reasons, every effort (e.g. telephone, e-mail, letter) should be made to contact the subject/pre-designated contact as specified in [Section 9.1.3](#). This contact should preferably be done according to the study visit schedule.

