**Use Dec31yyyy**

Case 3: Only Year(yyyy) of the dose end date is available and yyyy = the year of EOT date:

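### The SAP's rule for a missing last-dose date is written per drug but tied to the end of all treatment, so it can date a last spartalizumab infusion months after spartalizumab stopped

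*SAP*

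**What the plan says.** SAP 5.1.1.1 sets one rule at component level: "The following rule should be used for the imputation of date of last administration for a given study treatment component". The imputed value depends on what is known:

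- Scenario 1, no EOT page: "In this case, the cut-off date should be used as the last dosing date for exposure calculations".
- Scenario 2, Case 1: "Case 1: The date of last administration is completely missing, and the EOT visit date is complete, then this latter date should be used".
- Year known but nothing else, and earlier than the EOT year (Case 2): "Use Dec31yyyy".
- Case 3, only the year known and equal to the EOT year: the EOT date.
- Case 4, year and month known, in the EOT year but an earlier month: the last day of that month.

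The one check afterwards is a lower bound: an imputed date before the start of its own record is moved up to that start. If the first administration date is missing, nothing is imputed.

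Protocol 9.1.1 ties EOT to the whole regimen: "An end of treatment visit will be performed when subjects permanently discontinue the study treatment to which they were assigned at study entry". Protocol 8.5.2.3 treats EOT and the end of spartalizumab as two events, with sampling "at the time of study treatment discontinuation (EOT visit) or when spartalizumab treatment is discontinued". Protocol 6.7.2 states: "Following the study enrollment halt, spartalizumab treatment has been discontinued in all ongoing subjects". The Study Update in Amendment 1 adds: "The patients who were on combination treatment have discontinued spartalizumab and are continuing on capmatinib single agent since the enrollment halt".

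SAP 2.4.1.1 adds 27 days to the last spartalizumab record to obtain the end of exposure, cut short by death or loss to follow-up. SAP 2.4.1.3 uses that duration as the denominator of dose intensity (DI).

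**The concern.** The rule suits a tablet taken continuously until EOT. Spartalizumab is a short infusion every 28 days, and it was stopped while capmatinib went on. For that drug, the cut-off, the EOT date and 31 December say little about the last infusion, and nothing stops the imputed date from falling after spartalizumab had ended.

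If that happens, spartalizumab exposure is too long, and DI and relative dose intensity (RDI) are too low. Dose intensity is a named tolerability endpoint in Protocol Table 2-1 and SAP Table 1-1, and enrollment was halted for lack of tolerability of the combination. A low spartalizumab RDI produced by imputation could be mistaken for poor tolerance. The listing of medications started up to 150 days after the last spartalizumab dose (SAP 2.4.4.3) also depends on this date.

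**Working it through.** **Reproducing the SAP's own figures**

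- Spartalizumab DI = 28 × cumulative dose / days of exposure. Two infusions over 56 days: 28 × 800 / 56 = 400 mg/cycle, as in SAP 2.4.1.3.
- Expected infusions: the 60-day example in SAP 2.4.1.2 gives three, which is 60/28 rounded up.
- The formula in SAP 2.4.1.1 does not give the 56 days. Infusions on days 1 and 29 end exposure on day 29 + 27 = 56. The capmatinib formula adds 1 but the spartalizumab formula does not, so the result is 56 − 1 = 55 days and DI is 28 × 800 / 55 = 407. The figures below use the inclusive count, which matches the worked example.

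**Illustrative subject under Case 2** (assumed: four 400 mg infusions, 08-Apr to 01-Jul-2021; last end date known only as 2021; EOT in 2022)

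- True exposure: 84 + 27 + 1 = 112 days. DI = 28 × 1600 / 112 = 400. Expected infusions 112/28 = 4, so RDI = 1600/1600 = 100%.
- Imputed date 31-Dec-2021: 267 + 27 + 1 = 295 days. DI = 28 × 1600 / 295 = 152. Expected infusions 295/28 = 10.5, rounded up to 11, so RDI = 1600/4400 = 36%.
- Without the +1, the durations are 111 and 294 days and DI is 403.6 and 152.4. The conclusion does not change.
- Over the 28 subjects treated with the combination, this one subject raises mean exposure by (295 − 112)/28 = 6.5 days and moves 1/28 = 3.6% of them into the lowest RDI category (below 50%).

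**Sensitivity to the gap between last infusion and imputed date** (gaps and infusion counts are assumptions)

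| Infusions | Gap (days) | Exposure (days) | DI (mg/cycle) | RDI |
|---|---|---|---|---|
| 2 | 0 | 56 | 400 | 100% |
| 2 | 40 | 96 | 233 | 50% |
| 2 | 77 | 133 | 168 | 40% |
| 2 | 150 | 206 | 109 | 25% |
| 6 | 150 | 318 | 211 | 50% |

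The gaps are anchored in the documents. From the halt on 28-Jul-2021 it is 40 days to the 06-Sep-2021 status date and 77 days to the amendment date of 13-Oct-2021. Protocol 9.2.1 requires safety assessments up to 150 days after the last spartalizumab dose before a transfer. Taking EOT as the transfer date is an assumption.

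**Who could be affected**

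The Study Update gives 28 subjects on the combination, 3 who began capmatinib alone, and 19 still on capmatinib on 06-Sep-2021. Between 19 − 3 = 16 and 19 of the 28 (57% to 68%) were therefore still on capmatinib, and a large overshoot is possible for them. The other 9 to 12 had stopped by then. With EOT within 7 days of last treatment (Protocol Appendix 1, 16.1.4.2), their EOT date falls at most about 40 + 7 = 47 days after the halt.

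**The case against.** The strongest reply is that the rule may never be triggered for spartalizumab. Infusions are given on site, the IRT is contacted at each administration (Protocol 6.6.1), and missing values are queried (Protocol 11.2). Nothing in the documents shows that a single infusion date is missing or year-only. This stands, and it limits the size of the point.

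Several features also narrow its reach:

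- Imputation is blocked when the first administration date is missing, which protects subjects who never received spartalizumab.
- Case 4 errs by at most about a month.
- Scenario 1 should seldom apply, because only a final report at study completion is planned (SAP 2.1).
- Subjects who stopped both drugs together have an EOT date close to their last dose.
- Derived-variable rules sit in a separate programming specification, which may already bound the date. That cannot be checked here.

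A reader might infer that the last infusion is dated months late for every subject, because spartalizumab was stopped in every ongoing subject. The documents do not support that: the rule acts only on a missing or partial date, and the long error arises only where capmatinib continued well beyond spartalizumab.

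A reader might also take 28-Jul-2021 as the spartalizumab stop date. The protocol gives it as the enrollment-halt date and places the discontinuation immediately after it, without a date.

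None of this repairs the rule. When it is triggered, it can produce a date on which no infusion was possible. Where only the end date of an infusion is missing, the rule also passes over a start date already in the record.

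**Conclusion.** The point holds as a minor defect in the SAP text. In a subject who continued capmatinib after spartalizumab ended, Scenario 1 and Cases 1 to 3 can impute a spartalizumab date up to months too late, with no upper bound. A fully dosed subject could then show an RDI of 25% to 50% in the examples with a gap of 40 days or more. These sizes rest on assumed infusion counts and EOT dates, on the inclusive day count, and on expected infusions being rounded up over the full exposure period.

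The number of affected subjects is unknown and may be zero. The consequence is confined to descriptive spartalizumab exposure, DI and RDI, and to the 150-day medication listing. A reader might infer that efficacy or the main safety tables are at risk. They are not: ORR, DCR and PFS do not use this date, and the on-treatment period runs from the last dose of either drug (SAP 2.1.1.6), which in these subjects is capmatinib.

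**What to change.** Change SAP 5.1.1.1 as follows:

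1. Limit the present rule to capmatinib.
2. For spartalizumab, set a missing infusion end date equal to the start date of the same record.
3. Resolve any other missing or partial spartalizumab date to no later than the earlier of the recorded spartalizumab discontinuation date and the EOT date. Do not use 28-Jul-2021 as a fixed cap.

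Also add 1 to the spartalizumab duration formula in SAP 2.4.1.1, so that it yields the 56 days of the example in 2.4.1.3.

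The cost is a few sentences in the SAP and a small programming change, with no new data collection. SAP section 1 provides for an amendment if the change is made before database lock and an addendum if after. A count of missing or partial spartalizumab dates would show whether any result changes.

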**Use Dec31yyyy**

Case 3: Only Year(yyyy) of the dose end date is available and yyyy = the year of EOT date:

**Use EOT date**

Case 4: Both Year(yyyy) and Month (mm) are available for the date of last administration, and yyyy = the year of EOT date and mm < the month of EOT visit:

**Use last day of the Month (mm).**

After imputation, compare the imputed date with the start date of that specific record, if the imputed date is < start date of that record

**Use the start date of that record.**

Subjects with missing start dates are to be considered missing for all study treatment component related calculations described in [Section 2.1.1.2](#) and no imputation will be made. If the date of first administration is missing, then the date of last administration should not be imputed.

##### 5.1.1.2 Data Imputation of the first administration

Subjects with missing start dates are generally considered missing for all study treatment component related calculations described in [Section 2.1.1.2](#) and no imputation will be made. If the date of first administration is missing, then the date of last administration should not be imputed.

### 5.1.2 AE date imputation

A missing AE start date will be imputed using the logic matrix described in [Table 5-1](#)

**Table 5-1** Imputation rules for a partially missing AE start date

	AEM missing	AEM<TRTM	AEM=TRTM	AEM>TRTM
AEY missing	Not imputation	Not imputation	Not imputation	Not imputation
AEY<TRTY	(D)	(C)	(C)	(C)
AEY=TRTY	(B)	(C)	(B)	(A)
AEY>TRTY	(E)	(A)	(A)	(A)

AEM=Month AE started, AEY=Year AE started

TRTM=Month treatment started, TRTY=Year treatment started

[Table 5-2](#) is the legend to the logic matrix shown in [Table 5-1](#) and details the relationship of AE start date to study treatment start date.

**Table 5-2** Imputation legend and AE/treatment start date relationship

AE start date relationship	Imputation
(A) After treatment start or uncertain	MAX(01MMMMYYYY, TRTSDT+1)
(B) Uncertain	TRTSDT+1
(C) Before treatment start	15MMMMYYYY
(D) Before treatment start	01JULYYYY
(E) After treatment start	01JANYYYY

Before treatment start: Partial date indicates AE start date is prior to treatment start date.

After treatment start: Partial date indicates AE start date is after treatment start date.

Uncertain: Partial date insufficient to determine relationship of AE start date to treatment start date.

No imputation will be performed for missing/incomplete AE end dates. AE with uncertain relationship will be considered as on-treatment AE.

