### 2.1.1.6 On-treatment assessment/event and observation periods

For all safety analyses, the overall observation period will be divided into three mutually exclusive segments:

- ***pre-treatment period***: from day of patient's informed consent to the day before first administration of study treatment
- ***on-treatment period***: from date of first administration of study treatment to 30 days after date of last actual administration of any study treatment (including start and stop date)
- ***post-treatment period***: starting at day 31 after date of last administration of study treatment

If dates are incomplete in a way that clear assignment to pre-, on-, post-treatment period cannot be made, then the respective data will be assigned to the on-treatment period.

Safety summaries will primarily include only data from the on-treatment period. Select summaries of related adverse events and death will be produced for the combined on-treatment and post-treatment periods of study treatment (see [Section 2.8.1](#) and [Section 2.8.2](#)).

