### 2.8.1 Adverse events (AEs)

Adverse event (AE) summaries will include all AEs occurring during on-treatment period. All AEs collected in the AE eCRF page will be listed along with the information collected on those AEs e.g., AE relationship to study drug, AE outcome etc. AEs starting during the post-treatment period will be flagged in the listings.

Adverse events (AEs) will be summarized by number and percentage of subjects having at least one AE, having at least one AE in each primary system organ class (SOC) and for each preferred term (PT) using MedDRA coding. A subject with multiple occurrences of an AE will be counted only once in the respective AE category. A subject with multiple CTCAE grades for the same preferred term will be summarized under the maximum CTCAE grade recorded for the event.

AE with missing CTCAE grade will be included in the 'All grades' column of the summary tables.

In AE summaries by primary SOC and PT, the primary SOC will be presented alphabetically and the PT will be sorted within primary SOC in descending frequency. Table by either primary SOC or PT will be sorted in descending frequency.

The following adverse event summaries will be produced for all subjects:

- Overview of adverse events summarized by relationship and deaths (number and % of subjects who died, with any AE, any SAE, fatal SAEs, AEs leading to dose reduction/interruptions, AE leading to treatment discontinuation)
- AEs by SOC and PT, summarized by relationship (all AEs and AEs related to study treatment).
- SAEs summarized by relationship (all SAEs and SAEs related to study treatment) and severity.
- AEs leading to study treatment discontinuation (all AEs and AEs related to study treatment).
- AEs leading to study treatment dose reduction/interruption.

The following listings will be produced:

- All adverse events (safety set)
- All serious adverse events (safety set) (including those from the pre and post-treatment periods)
- Adverse events among subjects who were not treated (screening failure subjects)

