### 5.1.3 Concomitant medication date imputation

The imputation of a concomitant medication start date will follow the same conventions as for an AE start date (see [Section 5.1.2](#)). No imputation will be performed for concomitant medication end dates.

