##### End date

Imputed date = min (start date of study treatment, last day of the month), if day is missing.

Imputed date = min (start date of study treatment, 31DEC), if month and day are missing.

If the end date is not missing and the imputed start date is after the end date, use the end date as the imputed start date.

If both the start date and the end date are imputed and if the imputed start date is after the imputed end date, use the imputed end date as the imputation for the start date.

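### The SAP's start-date imputation for adverse events and concomitant medications ignores a known end date before first dose, so a few pre-treatment records can be given a start after their end and counted as on-treatment

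*SAP*

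**What the plan says.** SAP 5.1.2 (Tables 5-1 and 5-2) sorts partial AE start dates into classes by comparing the start month and year with those of first dose. Class (B) holds records whose month and year equal those of first dose, and records with only a year that equals the first-dose year. These get first dose plus one day. The class is judged from the start date only: "Uncertain: Partial date insufficient to determine relationship of AE start date to treatment start date". Then "AE with uncertain relationship will be considered as on-treatment AE". The one statement about end dates is "No imputation will be performed for missing/incomplete AE end dates".

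SAP 5.1.3 adds: "The imputation of a concomitant medication start date will follow the same conventions as for an AE start date".

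Four other places in the SAP bear on this:

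- **2.1.1.6** defines the on-treatment period as "from date of first administration of study treatment to 30 days after date of last actual administration of any study treatment". It confines the on-treatment default to one case: "If dates are incomplete in a way that clear assignment to pre-, on-, post-treatment period cannot be made".
- **2.4.4.3** describes concomitant therapy as therapy that overlaps with treatment. Its summaries, however, take in any medication whose start falls on the first-dose date or later, up to 30 days after last dose.
- **5.1.3.1** has an ordering check, for prior therapies only: "If the end date is not missing and the imputed start date is after the end date, use the end date" as the imputed start.
- **5.1.1.1** has a similar check for study drug: an imputed last-dose date may not precede the start of its own record.

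**The concern.** When the timing of an AE is truly unknown, placing it on-treatment is a sound conservative convention. The fault is narrower. A complete end date before first dose settles the timing, yet the class (B) rule overrides it with a date after first dose. The resulting record cannot be true, because it ends before it starts.

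The period assignment matters because "Adverse event (AE) summaries will include all AEs occurring during on-treatment period". Protocol 12.5.2.2 counts an event as treatment-emergent if it begins after first dose, or was present before and worsened. An event already over by first dose is neither. For medications, a course finished before first dose would enter the concomitant tables through its imputed start, including the table of medications given with immunosuppressive intent. SAP 2.8.1 also counts AE occurrences for public posting from the gap between one event's end and the next one's start, which a reversed record distorts.

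Affected records are possible. Protocol 10.1.1 collects AEs from main consent, and Protocol 8 sets screening at Day -28 to Day -1.

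**Working it through.** The plan states no figure on this point, so there is none to reproduce. The check applies Tables 5-1 and 5-2 to records with a known end date.

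**General result.** Let F be the first-dose date, S the imputed start and E the known end date.

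- Class (B): S = F + 1, so S is always after F and the record is always on-treatment.
- If E is before F, then E ≤ F − 1 and S − E ≥ 2 days. The start always falls after the end.
- Duration = E − S + 1 = E − F, which is always negative.

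**Examples**, with first dose on 20 March 2021 (an illustrative date). The bound is the 5.1.3.1 check: start = the earlier of S and E.

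| Recorded start | Known end | Class | Imputed start | Duration (days) | Period as written | Start with bound | Period with bound |
|---|---|---|---|---|---|---|---|
| March 2021 | 10 March 2021 | B | 21 March | −10 | on-treatment | 10 March | pre-treatment |
| 2021 only | 10 March 2021 | B | 21 March | −10 | on-treatment | 10 March | pre-treatment |
| 2021 only | 25 February 2021 | B | 21 March | −23 | on-treatment | 25 February | pre-treatment |
| February 2021 | 10 March 2021 | C | 15 February | 24 | pre-treatment | 15 February | pre-treatment |

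The last row marks the scope: class (C) records, and likewise class (D), stay pre-treatment. If E equals F, the bound gives S = F and the record stays on-treatment.

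**How often the rule misplaces such a record, once one exists.** Assume that all start and end day pairs within Day -28 to Day -1 are equally likely, and that first dose falls on any day of 2021. Then about 38% of records that ended before first dose move on-treatment if only the start day is missing, and about 95% if day and month are missing. Both shares run from 0% to 100% depending on the first-dose date. With the bound, both are 0%. These are conditional shares and do not say how many such records the trial has.

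**Size in a table.** Protocol 4.1 gives 31 treated subjects. One subject is 1/31 = 3.2%; two are 2/31 = 6.5%. SAP 2.8.1 posts non-serious AEs with incidence above 5%, so where one subject genuinely has a term, one misplaced subject would lift it from 3.2% to 6.5% and across that line.

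**The case against.** The strongest reply is that SAP 2.1.1.6 already governs period assignment. A complete end date before first dose makes the assignment clear, so the record would be pre-treatment and only an odd-looking start date would remain. This does not settle the matter. SAP 5.1.2 is the specific AE rule, defines uncertainty from the partial start date alone, and assigns the period outright. The two sections conflict, and nothing says which prevails. The same holds for medications: the overlap definition in 2.4.4.3 would exclude a finished course, but the inclusion rule below it is met by the imputed start.

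A second reply is that the record is rare, and this stands. The AE must begin and end between consent and first dose, have a complete end date, and lack a start day in the first-dose month (or have only the year). Conditions present at consent go to medical history and start and end dates are to be recorded (Protocol 10.1.1), and missing values are queried (Protocol 11.2). A medication with a year-only start in an earlier year is class (D) and stays pre-treatment.

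A third is that the SAP introduction leaves derived-variable detail to a programming specification, which is not among the documents. A check may exist there. The SAP itself contains none for these data, although it writes one out for prior therapies and for study drug.

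Finally, any error overstates toxicity. That is true, but it does not justify a reversed record when the end date is known.

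**Conclusion.** The point holds as a drafting gap of small consequence. It is limited to class (B) AEs and concomitant medications with a complete end date before first dose. Their number is unknown and probably very small. The 3.2 points is a ceiling for a given AE row: SAP 2.8.1 counts a subject once per category, so a row does not move if the subject has another on-treatment event in it. ORR, DCR and PFS do not use these dates.

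Because enrollment was halted for lack of tolerability, a reader might infer that the tolerability findings are materially inflated, or that finished steroid courses will commonly appear as concomitant. The documents do not support either. They show no such record, and the idea that year-only medication starts are common is an assumption. Most tables of treatment-related AEs and of AEs leading to dose reduction, interruption or discontinuation should also be unaffected, since an event over before first dose should neither be attributed to treatment nor prompt a dose action.

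**What to change.** Make two additions to the SAP:

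1. In 5.1.2 and 5.1.3, extend the sentence already in 5.1.3.1: if the end date is known and the imputed start is later, take the end date as the start.
2. In 5.1.2, apply the on-treatment default only when the end date is missing, incomplete, or on or after first dose. A record with a complete end date before first dose is then pre-treatment, in line with 2.1.1.6 and 2.4.4.3.

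Records of truly unknown timing keep the conservative default. The first addition also corrects a class (C) record that ended before the 15th of its month, where the imputed start falls after the end although the period is right. The cost is about a sentence in each section and one line of code, with the programming specification aligned. No new data are needed.
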